Information on transfusions will be listed by patient and visit/time.

8 Statistical methods for Biomarker data

Corporate Confidential Information

Handling of LLOQ and ULOQ

Biomarker data are reported as concentration results, measured using a specific assay with a working range defined by the two limits: Lower limit of quantification (LLOQ) and Upper limit of quantification (ULOQ). Values which fall below the LLOQ or above the ULOQ are reported as $< \text{LLOQ} * \text{dilution factor}$ (dilution factor: if sample diluted and concentration measured still below LLOQ) and $> \text{ULOQ} * \text{dilution factor}$, respectively.

To ensure that biomarkers only have numerical values, censored values will be imputed as follows

- Values below the LLOQ are replaced by $\text{LLOQ}/2$.
- Values above the ULOQ are replaced by ULOQ.

Imputed values are used for summary statistics, inferential analyses and plots (with a special symbol). Values below LLOQ and values above ULOQ are shown as such in the listings. In the summary table, the frequency (n, %) of values below the LLOQ and above the ULOQ, respectively, will be included.

If the proportion of imputed data is more than 20% for any treatment group at any time point, a footnote is added to the summary statistics table stating that the proportion of values outside

the limits of quantification is more than 20% for some treatment groups at some time points and that in such cases summary statistics may be heavily biased.

If the proportion of imputed data for a given biomarker, across all treatment groups and time points, is more than 50%, no summary statistics are provided and the data are only listed.

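### Minor: the biomarker imputation rule omits the dilution factor, so as written a diluted sample still above range is imputed below its own reported limit

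*SAP*

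**What the plan says.** All the relevant text is in SAP section 8, under Handling of LLOQ and ULOQ.

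- **Definition.** LLOQ and ULOQ belong to the assay: results are "measured using a specific assay with a working range defined by the two limits".
- **Reporting.** A result outside the range is reported as < LLOQ × dilution factor or > ULOQ × dilution factor. The factor is explained only for the lower end: "dilution factor: if sample diluted and concentration measured still below LLOQ".
- **Imputation.** The bullets are introduced by "To ensure that biomarkers only have numerical values, censored values will be imputed as follows". A result below range becomes LLOQ/2. For the upper end the rule is "Values above the ULOQ are replaced by ULOQ". Neither bullet contains the dilution factor.
- **Use.** Imputed values go into summary statistics, inferential analyses and plots, where they carry a special symbol. Listings keep the censored result: "Values below LLOQ and values above ULOQ are shown as such in the listings".
- **Disclosure.** Summary tables give n (%) below and above range. A footnote is added "If the proportion of imputed data is more than 20% for any treatment group at any time point", warning that "in such cases summary statistics may be heavily biased". A biomarker with more than 50% imputed values overall is listed only.

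**The concern.** The section writes the assay limit and the dilution-adjusted limit as two different quantities, then uses only the first for imputation. Nothing visible redefines the symbols in between.

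At the upper end this gives an impossible value. A diluted sample reported as > ULOQ × DF is known to exceed that limit, yet it is set to ULOQ, which is lower whenever DF exceeds 1. It can then fall below diluted samples that were quantified between ULOQ and ULOQ × DF, so the highest sample in a cell need not be the highest value analysed.

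At the lower end the rule is only inconsistent. LLOQ/2 still lies below LLOQ × DF and so remains possible, but it is not half of the limit that was reported.

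At stake are biomarker means and any geometric means, which are pulled down, and agreement between outputs: for the same sample, the plotted value and the limit in the listing would differ by the factor DF.

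**Working it through.** The SAP gives no figure to reproduce here. It also shows no dilution factors, assay limits or biomarkers, so **every DF, ULOQ and sample value below is an assumption**.

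**Inputs from SAP section 8:** reported upper limit ULOQ × DF; imputed value ULOQ; reported lower limit LLOQ × DF; imputed value LLOQ/2; footnote when more than 20% of a cell is imputed.

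**1. One sample.**
- Upper end: imputed ÷ reported limit = ULOQ ÷ (ULOQ × DF) = 1/DF.
- Lower end: imputed ÷ half the reported limit = (LLOQ/2) ÷ (LLOQ × DF/2) = 1/DF.
- The ratio is 1.00 at DF 1, 0.50 at DF 2, 0.10 at DF 10 and 0.01 at DF 100.

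**2. One treatment-by-time cell.** Let k of n values be diluted samples still above range, all with the same DF.
- Shortfall of the mean ≥ (k/n) × ULOQ × (DF − 1).
- Geometric mean too low by a factor ≥ DF^(k/n).

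Both are minimum figures, because the true value exceeds ULOQ × DF.

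**3. How large k can be without the cell itself meeting the footnote trigger.** The trigger needs k/n > 0.20. The largest k that does not meet it is 0 for n = 4, 1 for n = 5, 2 for n = 10 and 4 for n = 20.

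**4. Results.**

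| DF | Mean shortfall, k/n = 0.20 | Geometric mean factor | Mean shortfall, 1 of 20 | Geometric mean factor |
|---|---|---|---|---|
| 1 | 0 | 1 | 0 | 1 |
| 2 | 0.2 × ULOQ | 1.15 | 0.05 × ULOQ | 1.04 |
| 10 | 1.8 × ULOQ | 1.58 | 0.45 × ULOQ | 1.12 |

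**5. Example.** ULOQ = 100, DF = 2; four samples quantified at 30, 60, 90 and 150, and one reported as > 200.

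| | Rule as written (fifth value 100) | Reported limit (fifth value 200) |
|---|---|---|
| Mean | 430/5 = 86 | 530/5 = 106 |
| Geometric mean | 75.4 | 86.6 |
| SD | 45.1 | 68.8 |
| Median | 90 | 90 |
| Maximum | 150 | 200 |

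The difference in means, 20, equals 0.2 × 100 × (2 − 1), as step 2 gives. The sample known to exceed 200 is analysed as 100, below the quantified 150. One of five is exactly 20%, so this cell does not itself trigger the footnote.

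**The case against.** The strongest reply is that ULOQ in the bullet is shorthand for the reported limit. The bullets follow directly on the reporting rule and act on its output, and the sentence on listings uses the same short form for the reported censored result. This reading is tenable, and it would remove the problem. But the dilution factor is written out immediately before and omitted here, so two programmers could code the rule differently.

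A related argument is that a strictly literal reading would also replace quantified results above the bare ULOQ. In the example, 150 would become 100, the mean would be 380/5 = 76, and two of five values (40%) would be imputed, which triggers the footnote. On this view the example reads half the sentence literally and half as shorthand. That does not succeed: the lead-in limits imputation to censored values, so a quantified 150 is left alone and the reversed ranking stands.

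The following points do stand:
- The lower-end change is for consistency only.
- The biomarker details are redacted, so whether any sample is affected cannot be seen.
- SAP section 1.1 describes an analysis of reduced scope, and SAP section 6 has the efficacy estimands listed, not analysed.
- Imputing the reported limit is itself a lower bound and still biases downward, though by less.
- The safeguards are real. The footnote applies to the whole table, so one cell above 20% adds it. With up to six treatment groups in summary tables (SAP section 4), small cells that trigger it are plausible. However, the safeguards disclose imputation; they do not correct the number.

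**Conclusion.** The point holds and is minor. As written, the upper-end rule contradicts the reporting rule beside it whenever a diluted sample remains above range: the imputed value is 1/DF of a limit the sample exceeds. If the bullets are shorthand, the fault is an unstated definition that leaves two readings apart by the factor DF.

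The size in this trial is unknown and may be zero. It depends on dilution having been used and on diluted samples staying above range, neither of which the SAP shows. The consequence is confined to the biomarker summaries, plots and any biomarker inference. Undiluted samples are unaffected, and nothing visible carries the imputed values into the efficacy estimands.

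**What to change.** In the two imputation bullets of SAP section 8, refer to each sample's reported limit: above range, impute ULOQ × dilution factor; below range, impute (LLOQ × dilution factor)/2; take the factor as 1 for an undiluted sample. If the bullets already mean the reported limit, one sentence saying so is enough.

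The cost is a few words. No new data are needed, because the reported < or > result already contains the factor.
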